9.6. Statistical Analyses

This section provides a summary of the planned statistical analyses of the primary and secondary objectives in Phase A (randomized, blinded). The SAP will be developed and finalized before the first planned analysis ([Section 9.7](#)).

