9.7. Planned Analyses

The planned analyses of immunogenicity and safety will be conducted after participants have completed Day 29 and Month 3 visit assessments. Analyses of the Month 6 and Month 12 visit including the Phase B (open-label, observational) part of the study will be exploratory. The final analysis of all endpoints will be performed after all participants have completed or discontinued from the study. Results of this analysis will be presented in a final CSR.

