4.6. Blinding and Unblinding

As the appearance of the study vaccines differs, enrollment will be observer-blinded as to treatment assignment.

The investigator, clinic staff, study participants, site monitors, and Sponsor personnel (or its designees) will be blinded to the IP administered until the study database is locked and unblinded for the final analysis. Once participants become eligible to obtain an additional booster outside of the study, they become eligible for optional unblinding and continue in Phase B of the study part they were enrolled. In Part 1, participants in either treatment arm are eligible to choose to be unblinded to study treatment after completion of the Month 6 visit. In Part 2, participants in either treatment arm are eligible to choose to be unblinded to study treatment after completion of the Month 3 visit. If a participant decides to obtain an additional booster, the booster would be obtained outside the study. Additionally, participants can choose to not be unblinded after completion of the Month 6 (Part 1) and Month 3 (Part 2) visits. All participants are encouraged to continue the study regardless of choosing to be unblinded or remain blinded and/or choosing to obtain an additional booster external to the study. The optional unblinding will be performed at the participant level by a study site member via the IRT system with all other site members remaining blinded to original treatment assignment.

At the planned analysis (see [Section 6.6](#)), pre-identified Sponsor team members and selected contract research organization (CRO) team members will be unblinded to conduct the analyses. Study participants, investigators, and blinded site personnel will remain blinded.

Planned primary analysis are described in [Section 6.6](#) of this SAP and Section 9.7 of the protocol. Participant-level unblinding will be restricted to an independent unblinded statistician and as needed, statistical programmer(s) performing the primary analysis, who will have no other responsibilities associated with the study.

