6.5.1.3. Derivation of Symptomatic SARS-CoV-2 Infection (COVID-19)

The incidence of symptomatic SARS-CoV-2 infection starting 14 days after randomization is an exploratory endpoint in Part 1 and a secondary endpoint in Part 2. Surveillance for COVID-19 symptoms will be conducted via safety calls throughout the duration of the study and blood draw from scheduled visits. Participants reporting certain COVID-19 symptoms will be arranged an unscheduled visit to collect an NP swab.

Symptomatic SARS-CoV-2 infection will be defined in the following two ways:

1. Protocol-defined COVID-19 case definition (primary case definition): Cases to be defined as meeting clinical criteria based on both symptoms of COVID-19 and positive RT-PCR test results as outlined in [Table 6](#).
2. CDC Case Definition of COVID-19 (secondary case definition): Cases will be identified as a positive post-baseline RT-PCR test result that is prompted by symptom(s), together with eligible symptoms, i.e., a positive PCR result of the eligible symptoms summarized below in [Table 7](#).

Table 6 Derivation of Symptomatic COVID-19 (primary case definition)

Post-baseline PCR results	Positive, AND
Systemic Symptoms	at least TWO of the following systemic symptoms : Fever ($\geq 38^{\circ}\text{C}/\geq 100.4^{\circ}\text{F}$), chills, muscle and/or body aches (not related to exercise), headache, sore throat, new loss of taste/smell; OR
Respiratory Symptoms	at least ONE of the following respiratory signs/symptoms: cough, shortness of breath and/or difficulty breathing, OR clinical or radiographical evidence of pneumonia.

Table 7 Derivation of Symptomatic COVID-19 (secondary case definition)

	COVID-19 (CDC criteria)
Post-baseline PCR results	Positive, AND
Systemic Symptoms	at least ONE of the following systemic symptoms: Fever ($\text{temperature} \geq 38^{\circ}\text{C}/\geq 100.4^{\circ}\text{F}$) or chills, fatigue, muscle and/or body aches (unrelated to exercise), headache, congestion or runny nose, new loss of taste or smell, sore throat, or vomiting or diarrhea; OR
Respiratory symptoms	at least ONE of the following respiratory signs/symptoms: cough, shortness of breath or difficulty breathing.

The date of documented COVID-19 (case) will be the later date of the eligible symptom(s) and date of positive PCR test and the two dates should be within 14 of each other. Specifically, for the primary definition, the date of the documented COVID-19 will be later date of:

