6.5.2. Analysis Method

The number and percentage of participants who had each type of event (i.e., an asymptomatic or a symptomatic SARS-CoV-2 infection) will be summarized in the PPSE.

As per Phase B, participants are allowed to receive an additional booster outside of the study. Participants who received this additional booster may be censored in the efficacy analyses at the time of booster, as outlined below.

The incidence rate of each type of event will be calculated as the number of cases divided by the total person-time. Person-time is defined as the total time from randomization date to the date of event, last date of study participation, censoring time, date of additional booster outside of the study or efficacy data cutoff date, whichever is earlier.

The 95% CI of the incidence rate will be calculated using the exact method (Poisson distribution) and adjusted by person-time.

Vaccine efficacy and the respective 95% CI will also be estimated.

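### SAP 6.5.2 does not stop efficacy cases or person-time at optional unblinding, so an unstated, participant-selected share of the Part 2 secondary efficacy comparison can be open-label

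*SAP*

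**What the plan says.** SAP 6.5.2 runs person-time from randomization to the event or to "last date of study participation, censoring time, date of additional booster outside of the study or efficacy data cutoff date, whichever is earlier". Neither censoring time nor the efficacy data cutoff is defined. Just before this, the same section says that participants who take an outside booster "may be censored in the efficacy analyses at the time of booster".

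SAP 6.5.1.1 to 6.5.1.3 define cases by symptoms, RT-PCR and nucleocapsid serology, counted from 14 days after randomization. None of them closes the counting window at unblinding. SAP 6.5.1.3 says the symptomatic endpoint "is an exploratory endpoint in Part 1 and a secondary endpoint in Part 2".

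SAP 4.6 states: "In Part 2, participants in either treatment arm are eligible to choose to be unblinded to study treatment after completion of the Month 3 visit". Protocol 6.3.7 limits this to participants who report eligibility for an outside booster, and keeps blinded and unblinded participants on the same visit schedule.

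Protocol 9.6 introduces itself as a summary of the "planned statistical analyses of the primary and secondary objectives in Phase A (randomized, blinded"). Protocol 9.7 adds: "Analyses of the Month 6 and Month 12 visit including the Phase B (open-label, observational) part of the study will be exploratory". SAP 6.6 repeats this. SAP 6.1 and 6.5 allow optional exploratory efficacy analyses by Phase B subset, and one of these subsets is participants who were unblinded and took no outside booster.

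**The concern.** A Part 2 participant who is unblinded after Month 3 and takes no booster has no stated stopping point before the end of participation or the undefined cutoff. On the text as written, that open-label time and any cases in it enter the same estimate as the blinded time.

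The Part 2 titer objectives are limited to Day 29 or Month 3, and the Amendment 2 summary ties the removal of Month 6 to the open-label phase. The Part 2 infection objective has no such limit.

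Detection between visits starts with the participant: symptom recognition, local PCR or lateral flow testing, then an illness visit (Protocol 8.9.2), with eDiary prompts every two weeks (8.9.4). Someone who knows their arm may report, test or take exposure risks differently. Stopping only at the booster adds a second problem, which is my inference: once the arm is known, the decision to take an outside booster can depend on it, so censoring can differ by arm. The choice to be unblinded is made before the arm is known.

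The *may* wording is a separate defect. Person-time always ends at the booster. If later cases were still counted, the numerator would include events from time that is missing from the denominator.

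**Working it through.** The plan gives no efficacy event count, power or person-time figure, so there is nothing to reproduce. The check is how much person-time could be open-label.

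**Inputs from the documents**
- Day 85 is 84 days and Day 359 is 358 days after vaccination (schedule of events).
- Amendment 1, which created Part 2, is dated 03 Mar 2022 (Protocol 11.5.1).
- Amendment 2, which created optional unblinding, is dated 26 Aug 2022 (SAP 1).
- Estimated last completion is 07 Apr 2023 (synopsis).

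**Not in the documents, so assumed**
- u: share unblinded.
- b: share of those who then take an outside booster.
- g: days from unblinding to booster.
- No dropout, and person-time lost at events is ignored.

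**Ceiling by visit schedule.** Everyone unblinds right after Month 3 and nobody is boosted: (358 − 84)/358 = 274/358 = 76.5%.

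**Ceiling by calendar.** The estimated last completion implies a last vaccination near 07 Apr 2023 − 358 days = 14 Apr 2022. If Part 2 vaccination ran from 03 Mar to 14 Apr 2022, participants were 176 to 134 days past vaccination on 26 Aug 2022. The ceiling is then (358 − 176)/358 = 50.8% to (358 − 134)/358 = 62.6%. A last vaccination 14 days later (28 Apr 2022, s = 120) gives 238/358 = 66.5% for that participant.

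**Share with booster censoring.** With s = days from vaccination to unblinding:

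open = u[(1 − b)(358 − s) + b·g]

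blinded = (1 − u)·358 + u·s

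share = open/(open + blinded)

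Example with u = 0.5, b = 0.5, g = 14, s = 84: open = 0.5(137 + 7) = 72; blinded = 179 + 42 = 221; share = 72/293 = 24.6%.

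| u | b | g (days) | s = 84 | s = 134 | s = 176 |
|---|---|---|---|---|---|
| 100% | 0 | – | 76.5% | 62.6% | 50.8% |
| 100% | 50% | 14 | 63.2% | 47.0% | 35.8% |
| 100% | 90% | 14 to 30 | 32.3-39.3% | 20.7-26.9% | 14.9-20.4% |
| 50% | 0 | – | 38.3% | 31.3% | 25.4% |
| 50% | 50% | 14 | 24.6% | 19.5% | 15.5% |
| 50% | 90% | 14 to 30 | 8.3-11.0% | 6.6-9.1% | 5.5-7.8% |

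**When would it exceed half?** With no boosters, u must exceed 179/(358 − s): 65.3% at s = 84, 79.9% at s = 134, 98.4% at s = 176.

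**After the fix.** The open-label share is 0%. A participant unblinded right after Month 3 contributes 84/358 = 23.5% of scheduled time; one who stays blinded and unboosted contributes all 358 days.

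**The case against.** The strongest reply is that the text leaves room for the right analysis. Censoring time is listed separately from booster and cutoff, and neither it nor the cutoff is defined, so a stop at unblinding is not ruled out. This stands as a reason to call the defect a gap in definition. It does not supply the stop.

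Second, Protocol 9.6 is a scope sentence. A reader might infer a strict rule that secondary objectives use Phase A data only. The documents do not support that: the same section covers safety analyses of a primary objective whose endpoints run to end of study. What remains is a mismatch with the declared framing.

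Third, Phase B is labelled exploratory, and SAP 6.1 and 6.5 already foresee efficacy analyses by unblinded and boosted subset. This stands, but those analyses are optional and do not restrict the main estimate.

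Fourth, the scope for bias is limited. Swabs and surveillance blood are scheduled for everyone at Days 29, 85, 179 and 359. Symptomatic cases need RT-PCR, lateral flow results enter only sensitivity analyses, and other site staff stay blinded. This reduces the concern but leaves symptom-triggered testing between visits with the participant.

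Fifth, efficacy carries no hypothesis, alpha or power, and Protocol 9.6.2 makes vaccine efficacy conditional on enough cases. This limits the stakes to the interpretation of a secondary estimate.

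**Conclusion.** The point holds as a gap in the Part 2 secondary efficacy analysis. Nothing stated stops cases or person-time at optional unblinding, and the booster wording conflicts with the person-time definition. Part 1 efficacy is exploratory, so the issue matters mainly for Part 2.

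The size is unknown. The 77% and 51-63% figures are ceilings. The 8-39% range uses unblinding at Day 85 and covers two assumed cases: half unblinding with 50-90% boosted, and all unblinding with 90% boosted. Full unblinding with only 50% boosted would give 63%. Unblinding no earlier than the amendment date lowers all of these.

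A reader might infer that most of the comparison is open-label. That needs very high unblinding and limited uptake of the booster that is the reason for unblinding, and the documents give neither rate. A numerical bias in the rate ratio cannot be derived either: no reporting difference or its direction is stated, and share of person-time is not share of cases.

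**What to change.** In SAP 6.5.2, for the main Part 2 efficacy analysis:

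- Stop both case counting and person-time at the earliest of event, optional unblinding, outside COVID-19 booster, discontinuation or cutoff.
- Define the efficacy data cutoff, and define or delete censoring time.
- Change *may* be censored to *will* be censored, so that numerator and denominator cover the same time.
- Report follow-up beyond unblinding as a labelled exploratory Phase B analysis, next to the main estimate.

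The data burden is small: unblindings are tracked in the IRT (Protocol 6.3.7) and outside COVID-19 vaccines are recorded throughout the study. There are two real costs. The main estimate will have fewer events. Censoring at a time the participant chooses, tied to booster eligibility, may be somewhat informative; the retained full-follow-up analysis helps to check this.

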8. The participant will record data in the eDiary approximately 15 minutes after dosing while at the study site, with instruction provided by study staff. Study participants will continue to record in the eDiary each day after they leave the study site, preferably in the evening, on the day of dosing, and for 6 days following. Any solicited AR that is ongoing beyond Day 7 will be reported verbally by participants at the scheduled Safety Calls, until resolution. Adverse reactions recorded in eDiaries beyond Day 7 should be reviewed either via phone call or at the following study visit. Participants will be given thermometers to record their body temperatures and rulers to measure any injection site reactions.
9. Trained study personnel will call all participants to collect information relating to any MAAEs, AEs leading to study discontinuation, SAEs, AESIs, information on concomitant medications associated with those events, and any non-study vaccinations.
10. All concomitant medications and non-study vaccinations will be recorded through 28 days after vaccination, except authorized or investigational COVID-19 vaccine(s) given at any time during the study period should be recorded (Day 29 through EoS).

Table 2: Schedule of Events Part 2

Visit Number		1	2			3	4	5		6	USV
Type of Visit	C	C	C/SC	SC	SC	C	C	C	SC	C	C
Month Timepoint		M0				M1	M3	M6	M9	M12	Up to M12
Study Visit Day	Screening ¹	D1 (Baseline)	D8	D15	D22	D29	D85	D179	D269	D359/EoS	USV
Window Allowance (Days)	-28		+3	+3	+3	-3/+7	±7	±14	±7	±14	N/A
Days Since Vaccination	-	0	7	14	21	28	84	178	268	358	
ICF, demographics, concomitant medications, medical history ²	X										
Confirm participant meets inclusion and exclusion criteria	X	X									
Physical examination ³	X	X	X			X	X	X		X	X
Vital signs ⁴	X	X									X
Pregnancy testing ⁵	X	X									
Randomization		X									
Dosing											
Study injection (including 15-minute post-dosing observation period)		X									

Visit Number		1	2			3	4	5		6	USV
Type of Visit	C	C	C/SC	SC	C	C	C	SC	C	C	
Month Timepoint		M0			M1	M3	M6	M9	M12	Up to M12	
Study Visit Day	Screening ¹	D1 (Baseline)	D8	D15	D22	D29	D85	D179	D269	D359/EoS	USV
Window Allowance (Days)	-28		+3	+3	+3	-3/+7	±7	±14	±7	±14	N/A
Days Since Vaccination	-	0	7	14	21	28	84	178	268	358	
Surveillance for COVID-19											
Surveillance for COVID-19/Unscheduled visit ⁶	X	X	X	X	X	X	X	X	X	X	X
Nasopharyngeal swab ⁶		X				X	X	X		X	X
Blood for SARS-CoV-2 surveillance		X				X	X	X		X	

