6.5.1.2. Derivation of Asymptomatic SARS-CoV-2 Infection

The incidence of asymptomatic SARS-CoV-2 infection measured by RT-PCR and/or serology tests obtained at post-baseline visits counted starting 14 days after randomization

in participants with negative SARS-CoV-2 status pre-booster. This is an exploratory endpoint in Part 1 and a secondary endpoint in Part 2.

Asymptomatic SARS-CoV-2 infection is identified by absence of symptoms and infections as detected by RT-PCR or serology tests. Specifically:

- Absence of COVID-19 symptoms +/- 14 days from the positive test below
- AND at least one from below:
 - bAb level against SARS-CoV-2 nucleocapsid protein negative (as measured by Roche Elecsys) at Day 1 that becomes positive (as measured by Roche Elecsys) post-baseline, or
 - Positive RT-PCR test post-baseline (at scheduled or unscheduled/illness visits)

The date of documented asymptomatic infection is the earlier date of positive serology test result based on bAb specific to SARS-CoV-2 nucleocapsid due to infection, or positive RT-PCR at scheduled visits, with absence of symptoms.

The time to the asymptomatic SARS-CoV-2 infection will be calculated as:

Time to the asymptomatic SARS-CoV-2 infection = Date of asymptomatic SARS-CoV-2 infection – Date of randomization + 1.

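### Person-time for asymptomatic infection continues past the last scheduled swab and serology, so the absolute rate is too low in participants censored between samples

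*SAP*

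**What the plan says.** SAP 6.5.2 gives one rule for asymptomatic and symptomatic events: "The incidence rate of each type of event will be calculated as the number of cases divided by the total person-time". On the denominator it says "Person-time is defined as the total time from randomization date to the date of event", or, if sooner, "last date of study participation, censoring time, date of additional booster outside of the study or efficacy data cutoff date, whichever is earlier". No term refers to the last sample or the last negative test. The same section also says "Participants who received this additional booster may be censored in the efficacy analyses at the time of booster", so booster censoring is optional in one sentence and built into the person-time definition in another.

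SAP 6.5.1.2 describes asymptomatic infection as "measured by RT-PCR and/or serology tests obtained at post-baseline visits counted starting 14 days after randomization". Its case definition accepts "Positive RT-PCR test post-baseline (at scheduled or unscheduled/illness visits"). Its dating rule begins "The date of documented asymptomatic infection is the earlier date of positive serology test result based on bAb specific to SARS-CoV-2 nucleocapsid" and goes on to name, for PCR, scheduled visits only.

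In the schedules of events (Protocol 1.3, Tables 1 and 2), the row "Blood for SARS-CoV-2 surveillance" is marked after baseline only at Days 29, 85, 179 and 359. The routine nasopharyngeal swab falls on the same days. Protocol 8.9.2 adds an off-schedule route: a participant with a known close contact takes a lateral flow test, and a positive or equivocal result leads to an illness visit with a swab.

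**The concern.** A rate needs its numerator and denominator to cover the same time at risk. Symptomatic COVID-19 can be detected on any day, through safety calls, two-weekly eDiary prompts and illness visits, so stopping its clock at a booster or cutoff is right. A symptom-free infection usually surfaces only at the next scheduled sample and is dated there. If person-time stops before that sample, the case is normally lost but the days are kept.

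For example, take a Part 2 participant who is negative to Day 85, has a symptom-free infection on Day 110 and an outside booster on Day 165, and is N-positive on Day 179. The case is dated after the clock stopped and drops out, while Days 86 to 165 (80 days) remain in the denominator.

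Asymptomatic infection is a secondary endpoint in Part 2 and exploratory in Part 1. SAP 6.5 commits to incidence rates and to vaccine efficacy with a 95% CI. Part 2 participants may be unblinded after Month 3 and then choose a booster, so censoring between samples may be common. The sensitivity analyses in SAP 6.5.3 vary the population, the start of case counting and the test used, but not the end of person-time.

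**Working it through.** The documents give no case count, rate or person-time for this endpoint, so there is no figure of the plan's own to reproduce.

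**Inputs from the documents.** Samples are taken 28, 84, 178 and 358 days after injection (study day minus 1). The gaps are 28, 56, 94 and 180 days. The time after a last sample can therefore reach about 94 days following Month 3 and 180 days following Month 6.

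**Assumed inputs.** Booster date uniform over Days 150 to 270 (149 to 269 days after injection); uptake *p* of 30% to 90%; true symptom-free infection hazard of 15 per 100 person-years; all participants without a booster reach Day 359.

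**One participant.** For a booster *g* days after the Month 3 sample, the uncovered share of person-time is g/(84 + g):
- g = 14: 14/98 = 14.3%
- g = 30: 30/114 = 26.3%
- g = 60: 60/144 = 41.7%

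**Cohort, closed form (ignoring events).**
- Booster before the Month 6 sample: probability (178 − 149)/120 = 29/120; mean tail (149 + 178)/2 − 84 = 79.5 days.
- Booster after it: probability 91/120; mean tail (178 + 269)/2 − 178 = 45.5 days.
- Mean tail per boosted participant: (29 × 79.5 + 91 × 45.5)/120 = 53.7 days. Mean person-time per boosted participant: 209 days.
- Uncovered share: 53.7p / [209p + 358(1 − p)].

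| Uptake | Tail / person-time (days) | Uncovered share | Simulated rate ratio |
|---|---|---|---|
| 30% | 16.1 / 313.3 | 5.1% | 0.95 |
| 50% | 26.9 / 283.5 | 9.5% | 0.91 |
| 70% | 37.6 / 253.7 | 14.8% | 0.86 |
| 90% | 48.4 / 223.9 | 21.6% | 0.79 |

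The last column is the SAP rate divided by the rate with person-time ended at the last sample, with detection at the next scheduled sample. It is slightly nearer 1 than the closed form because participants with an event leave the denominator. At 70% uptake the rates are 12.6 and 14.7 per 100 person-years.

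Under scheduled-only detection, a case dated by the stop date is also dated by the last sample. The case count is then the same under either denominator, and the exact Poisson limits fall by the same factor as the rate.

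**Off-schedule detection.** If half of infections are found off-schedule, the ratios become about 0.97, 0.95, 0.93 and 0.90. At 70% uptake the SAP rule gives 13.8 and the truncated rule 14.8, against a true 15.

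**Ratio between arms, no true difference.** Equal uptake and timing give 1.00. Uptake of 70% against 40% gives 0.92 to 0.93 (0.96 with half found off-schedule); 60% against 50% gives about 0.97.

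**Any-infection endpoint.** With an added symptomatic hazard of 30 per 100 person-years (assumed; true total 45), the SAP rule gives 42.1 and 41.5 at 70% and 90% uptake. Truncating only the non-cases gives 48.7 and 51.5, a larger error.

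**The case against.** The strongest objection is that asymptomatic infection is not confined to scheduled samples. The case definition in SAP 6.5.1.2 admits PCR at unscheduled visits, and Protocol 8.9.2 supplies a route to such a swab without symptoms. A reader might infer that no case at all can be counted after the last sample. The documents do not support that: it is true of serology, but of PCR only if the dating sentence overrides the definition. The route does depend on a known contact and a positive or equivocal lateral flow test, so it shrinks the shortfall without removing it.

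A reader might also infer a much larger effect at the Day 29 or Month 3 data cut, where most participants would have a tail. SAP 6.6 and Protocol 9.7 list immunogenicity and safety for those analyses; all endpoints are analysed after participants complete or discontinue. By then, completers without a booster have a Day 359 sample and no tail.

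A bias between arms is possible but not shown, since the documents give no uptake or timing by arm. In Part 1 optional unblinding starts only after Month 6, so boosters from Day 150 do not model it. Finally, the booster-related effect presumes that the person-time definition, not the permissive sentence, governs booster censoring. All these limits stand. They narrow the point but leave its core intact.

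**Conclusion.** The point holds for the absolute asymptomatic rate and its exact Poisson limits, in participants censored between samples by an outside booster, end of participation or data cutoff. Relative to a rate ending at the last sample, the shortfall is about 5% to 21% at 30% to 90% uptake with no off-schedule detection, and roughly 3% to 10% if half of infections are found off-schedule. These sizes rest on the assumed booster dates, uptake and hazard; only the sampling gaps come from the documents. Time between two samples is not lost, because a seroconversion is picked up at the next visit. The ratio between arms moves only if booster uptake or timing differs by arm. No primary conclusion is affected. The change is worth making because this is a Part 2 secondary endpoint and the correction is cheap.

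**What to change.** Add to SAP 6.5.2, for asymptomatic SARS-CoV-2 infection only:

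> Person-time of participants without an event ends at the last scheduled RT-PCR or N-serology sample on or before the earliest of last study participation, outside booster and data cutoff. Only cases dated on or before that end date are counted; later off-schedule PCR cases are listed separately.

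The second sentence is needed so that numerator and denominator stop together. In SAP 6.5.1.2, make the definition and dating sentences agree on unscheduled PCR. In 6.5.2, define the censoring time and state whether booster censoring is applied or optional.

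Keep the present end date for symptomatic COVID-19. Do not carry the truncation into the any-infection analysis, where PCR cases in the tail would remain in the numerator while the tail time of non-cases was removed.

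The cost is a few SAP lines and a small programming change, with no new data. The downside is less person-time and slightly wider intervals for this endpoint.
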